9.6 Data Monitoring Committee (DMC)

An IDMC will be responsible for closely reviewing the safety and efficacy data from the interim analyses and for providing their recommendations on continuation of the study. The IDMC will meet to review after 10 and 20 participants have completed as well as at the time of the interim analyses (ie, after 60 and 150 participants have completed; see Section 9.5).

The detailed procedures and criteria of the interim analyses will be described in the DMC Charter.

10 Supporting Documentation and Operational Considerations

10.1 Appendix 1: Regulatory, Ethical, and Study Oversight Considerations

10.1.1 Regulatory and Ethical Considerations

- This study will be conducted in accordance with the protocol and with:
 - Consensus ethical principles derived from international guidelines including the Declaration of Helsinki and Council for International Organizations of Medical Sciences (CIOMS) International Ethical Guidelines.
 - Applicable International Council for Harmonisation (ICH) Good Clinical Practice (GCP) Guidelines.
 - Applicable laws and regulations.
- The protocol, protocol amendments, ICF, Investigator Brochure, and other relevant documents (e.g., advertisements) must be submitted to an IRB/IEC by the Investigator and reviewed and approved by the IRB/IEC before the study is initiated.
- Any amendments to the protocol will require IEC/IRB approval before implementation of changes made to the study design, except for changes necessary to eliminate an immediate hazard to study participants.
- The Investigator will be responsible for the following:
 - Providing written summaries of the status of the study to the IRB/IEC annually or more frequently in accordance with the requirements, policies, and procedures established by the IRB/EC.
 - Notifying the IRB/IEC of SAE or other significant safety findings as required by IRB/IEC procedures.
 - Overall conduct of the study at the site and adherence to requirements of 21 Code of Federal Regulations (CFR), ICH GCP guidelines, the IRB/IEC, European regulation 536/2014 for clinical studies (if applicable), and all other applicable local regulations.

10.1.2 Financial Disclosure

Information on financial disclosure can be found in the Investigator Site File.

10.1.3 Informed Consent Process

The Investigator or his/her representative will explain the nature of the study to the participant or his/her legally authorized representative and answer all questions regarding the study.

Participants must be informed that their participation is voluntary. Participants or their legally authorized representative will be required to sign a statement of informed consent that meets the requirements of 21 CFR 50, local regulations, ICH guidelines, Health Insurance Portability and Accountability Act (HIPAA) requirements, where applicable, and the IRB/IEC or study center.

The medical record must include a statement that written informed consent was obtained before the participant was enrolled in the study and the date the written consent was obtained. The authorized person obtaining the informed consent must also sign the ICF.

Participants must be re-consented to the most current version of the ICF(s) during their participation in the study.

A copy of the ICF(s) must be provided to the participant or the participant's legally authorized representative.

If a protocol amendment is required, the ICF may need to be revised to reflect the changes to the protocol. If the ICF is revised, it must be reviewed and approved by the appropriate IEC/IRB and signed by all participants subsequently enrolled in the study as well as those currently enrolled in the study.

For US participants who agree to tokenization, a separate optional ICF will be provided.

10.1.4 Data Protection

Participants will be assigned a unique identifier by the Sponsor. Any participant records or datasets that are transferred to the Sponsor will contain the identifier only; participant names or any information which would make the participant identifiable will not be transferred.

The participant must be informed that his/her personal study-related data will be used by the Sponsor in accordance with local data protection law. The level of disclosure must also be explained to the participant who will be required to give consent for their data to be used as described in the informed consent.

The participant must be informed that his/her medical records may be examined by Clinical Quality Assurance auditors or other authorized personnel appointed by the Sponsor, by appropriate IRB/IEC members, and by inspectors from regulatory authorities.

Data Protection for Tokenization information is addressed in the separate optional ICF (for US participants only).

10.1.5 Committees Structure

An IDMC will be responsible for closely reviewing the safety and efficacy data from the interim analyses and for providing their recommendations on continuation of the study (see Sections 9.5 and 9.6).

10.1.6 Data Quality Assurance

- All participant data relating to the study will be recorded on printed or electronic CRF unless transmitted to the Sponsor or designee electronically (e.g., laboratory data). The Investigator is responsible for verifying that data entries are accurate and correct by physically or electronically signing the CRF.
- The Investigator must maintain accurate documentation (source data) that supports the information entered in the CRF.
- The Investigator must permit study-related monitoring, audits, IRB/IEC review, and regulatory agency inspections and provide direct access to source data documents.
- Monitoring details describing strategies (e.g., risk-based initiatives in operations and quality such as Risk Management and Mitigation Strategies and Analytical Risk-Based Monitoring), methods, responsibilities and requirements, including handling of noncompliance issues and monitoring techniques (central, remote, or on-site monitoring) are provided in the Monitoring Plan.
- The Sponsor or designee is responsible for the data management of this study including quality checking of the data.
- The Sponsor assumes accountability for actions delegated to other individuals (e.g., Contract Research Organizations).
- Study monitors will perform ongoing source data verification to confirm that data entered into the CRF by authorized site personnel are accurate, complete, and verifiable from source documents; that the safety and rights of participants are being protected; and that the study is being conducted in accordance with the currently approved protocol and any other study agreements, ICH GCP, and all applicable regulatory requirements.
- Records and documents, including signed ICF, pertaining to the conduct of this study must be retained by the Investigator for at least 2 years after the last approval of a marketing application or 15 years from completion of the study, whichever is longer according to the relevant local laws and/or regulations. No records may be destroyed during the retention period without the written approval of the Sponsor. No records may be transferred to another location or party without written notification to the Sponsor.

- All data generated by the site personnel will be captured electronically at each study center using eCRFs. Data from external sources (such as laboratory data) will be imported into the database. Once the eCRF clinical data have been submitted to the central server at the independent data center, corrections to the data fields will be captured in an audit trail. The reason for change, the name of the person who performed the change, together with the time and date will be logged to provide an audit trail.
- If additional corrections are needed, the responsible monitor or data manager will raise a query in the electronic data capture (EDC) application. The appropriate staff at the study site will answer queries sent to the Investigator. The name of the staff member responding to the query, and time and date stamp will be captured to provide an audit trail. Once all source data verification is complete and all queries are closed, the monitor will freeze the eCRF page.
- The specific procedures to be used for data entry and query resolution using the EDC system/eCRF will be provided to study sites in a training manual. In addition, site personnel will receive training on the EDC system/eCRF.

10.1.7 Source Documents

Source documents provide evidence for the existence of the participant and substantiate the integrity of the data collected. Source documents are filed at the Investigator's site.

Data reported on the CRF or entered in the eCRF that are transcribed from source documents must be consistent with the source documents or the discrepancies must be explained. The Investigator may need to request previous medical records or transfer records, depending on the study. Also, current medical records must be available.

10.1.8 Study and Site Start and Closure

The study start date is the date on which the clinical study will be open for recruitment of participants. The first act of recruitment is the first participant signing the informed consent form and will be the study start date.

The Sponsor designee reserves the right to close the study site or terminate the study at any time for any reason at the sole discretion of the Sponsor. Study sites will be closed upon study completion. A study site is considered closed when all required documents and study supplies have been collected and a study site closure visit has been performed.

The Investigator may initiate study site closure at any time, provided there is reasonable cause and sufficient notice is given in advance of the intended termination.

Reasons for the early closure of a study site by the Sponsor or Investigator may include but are not limited to:

- Failure of the Investigator to comply with the protocol, the requirements of the IRB/IEC or local health authorities, the Sponsor's procedures, or GCP guidelines
- Inadequate recruitment of participants by the Investigator
- Discontinuation of further study intervention development

If the study is prematurely terminated or suspended, the Sponsor shall promptly inform the Investigators, the IECs/IRBs, the regulatory authorities, and any contract research organization(s) used in the study of the reason for termination or suspension, as specified by the applicable regulatory requirements. The Investigator shall promptly inform the participant and should assure appropriate participant therapy and/or follow-up

10.1.9 Publication Policy

- The results of this study may be published or presented at scientific meetings. If this is foreseen, the Investigator agrees to submit all manuscripts or abstracts to the Sponsor at least one month before submission. This allows the Sponsor to protect proprietary information and to provide comments.
- The Sponsor will comply with the requirements for publication of study results. In accordance with standard editorial and ethical practice, the Sponsor will generally support publication of multicenter studies only in their entirety and not as individual site data. In this case, a coordinating Investigator will be designated by mutual agreement.
- Authorship will be determined by mutual agreement and in line with International Committee of Medical Journal Editors authorship requirements.

10.1.10 Protocol Approval and Amendment

Before the start of the study, the study protocol and/or other relevant documents will be approved by the IEC/IRB/Competent Authorities, in accordance with local legal requirements. The Sponsor must ensure that all ethical and legal requirements have been met before the first participant is enrolled in the study.

This protocol is to be followed exactly. To alter the protocol, amendments must be written, receive approval from the appropriate personnel, and receive IRB/IEC/Competent Authority approval prior to implementation (if appropriate). In the US: Following approval, the protocol

amendment(s) will be submitted to the Investigational New Drug application under which the study is being conducted.

Administrative changes (not affecting the participant benefit/risk ratio) may be made without the need for a formal amendment. All amendments will be distributed to all protocol recipients, with appropriate instructions.

10.1.11 Liability and Insurance

10.1.11.1 Access to Source Data

Access to source data is described in the Clinical Site contract.

10.2 Appendix 2: The NEWS 2 Scoring System

Chart 1: The NEWS 2 scoring system

Physiological parameter	Score						
	3	2	1	0	1	2	3
Respiration rate (per minute)	≤8		9–11	12–20		21–24	≥25
SpO ₂ Scale 1 (%)	≤91	92–93	94–95	≥96			
SpO ₂ Scale 2 (%)	≤83	84–85	86–87	88–92 ≥93 on air	93–94 on oxygen	95–96 on oxygen	≥97 on oxygen
Air or oxygen?		Oxygen		Air			
Systolic blood pressure (mmHg)	≤90	91–100	101–110	111–219			≥220
Pulse (per minute)	≤40		41–50	51–90	91–110	111–130	≥131
Consciousness				Alert			CVPU
Temperature (°C)	≤35.0		35.1–36.0	36.1–38.0	38.1–39.0	≥39.1	

Abbreviations: CVPU: C=new onset confusion, disorientation or agitation, V=responds to voice, P=responds to pain, U=unresponsive; SpO₂=oxygen saturation.

Source: Royal College of Physicians. National Early Warning Score (NEWS) 2: Standardising the assessment of acute-illness severity in the NHS. Updated report of a working party. London: RCP, 2017.
<https://www.rcplondon.ac.uk/projects/outputs/national-early-warning-score-news-2>

10.3 Appendix 3: Clinical Laboratory Tests

The tests detailed in Table 1-1 will be performed by the local laboratory.

Protocol-specific requirements for inclusion or exclusion of participants are detailed in Section 5 of the protocol. Additional tests may be performed at any time during the study as determined necessary by the Investigator or required by local regulations.

Table 10-1 **Protocol-Required Laboratory Assessments**

Laboratory Assessments	Parameters			
Hematology	
CBC without differential:
 
White blood cell (WBC) count, red blood cell (RBC) count, hemoglobin, hematocrit, mean corpuscular volume, mean corpuscular hemoglobin, mean corpuscular hemoglobin concentration, red cell distribution width, platelet, mean platelet volume
 
Methemoglobin, nitrite
			
Clinical Chemistry ¹	Blood urea nitrogen Creatinine Glucose non-fasting	Potassium Sodium Chloride Bicarbonate/CO ₂	Aspartate Aminotransferase / Serum Glutamic-Oxaloacetic Transaminase Alanine Aminotransferase/ Serum Glutamic-Pyruvic Transaminase Alkaline phosphatase / Lactate dehydrogenase	Total and direct bilirubin Coagulation (PT/INR, aPTT)
Other Screening Tests	Highly sensitive urine human chorionic gonadotropin pregnancy test (for women of childbearing potential and pregnant women) ²			

Laboratory Assessments	Parameters
	The results of each test must be entered into the eCRF.

NOTES:

1 Details of liver chemistry stopping criteria and required actions and follow-up assessments after liver stopping or monitoring event are given in Section 7.1. All events of ALT $\geq 3 \times$ ULN and bilirubin $\geq 2 \times$ ULN ($>35\%$ direct bilirubin) or ALT $\geq 3 \times$ ULN and international normalized ratio (INR) >1.5 , if INR measured which may indicate severe liver injury (possible Hy's Law), must be reported as an SAE (excluding studies of hepatic impairment or cirrhosis).

2 Local urine testing will be standard for the protocol unless serum testing is required by local regulation or IRB/IEC.

Investigators must document their review of each laboratory safety report.

10.4 Appendix 4: Adverse Events: Definitions and Procedures for Recording, Evaluating, Follow-up, and Reporting

10.4.1 Definition of AE

AE Definition

• An AE is any untoward medical occurrence in a patient or clinical study participant, temporally associated with the use of a study intervention, whether or not considered related to the study intervention.• NOTE: An AE can therefore be any unfavorable and unintended sign (including an abnormal laboratory finding), symptom, or disease (new or exacerbated) temporally associated with the use of a study intervention.

Events Meeting the AE Definition

• Any abnormal laboratory test results (hematology, clinical chemistry, or urinalysis) or other safety assessments (e.g., ECG, radiological scans, vital signs measurements), including those that worsen from baseline, considered clinically significant in the medical and scientific judgment of the Investigator (e.g., not related to progression of underlying disease).• Exacerbation of a chronic or intermittent pre-existing condition including either an increase in frequency and/or intensity of the condition.• New conditions detected or diagnosed after study intervention administration even though it may have been present before the start of the study.• Signs, symptoms, or the clinical sequelae of a suspected drug-drug interaction.• Signs, symptoms, or the clinical sequelae of a suspected overdose of either study intervention or a concomitant medication. Overdose per se will not be reported as an AE/SAE unless it is an intentional overdose taken with possible suicidal/self-harming intent. Such overdoses should be reported regardless of sequelae.• "Lack of efficacy" or "failure of expected pharmacological action" per se will not be reported as an AE or SAE. Such instances will be captured in the efficacy assessments. However, the signs, symptoms, and/or clinical sequelae resulting from lack of efficacy will be reported as AE or SAE if they fulfill the definition of an AE or SAE.

Events NOT Meeting the AE Definition

- Any clinically significant abnormal laboratory findings or other abnormal safety assessments which are associated with the underlying disease, unless judged by the Investigator to be more severe than expected for the participant's condition.
- The disease/disorder being studied or expected progression, signs, or symptoms of the disease/disorder being studied, unless more severe than expected for the participant's condition.
- Medical or surgical procedure (e.g., endoscopy, appendectomy): the condition that leads to the procedure is the AE.
- Situations in which an untoward medical occurrence did not occur (social and/or convenience admission to a hospital).
- Anticipated day-to-day fluctuations of pre-existing disease(s) or condition(s) present or detected at the start of the study that do not worsen.

10.4.2 Definition of SAE

If an event is not an AE per definition above, then it cannot be an SAE even if serious conditions are met (e.g., hospitalization for signs/symptoms of the disease under study, death due to progression of disease).

An SAE is defined as any untoward medical occurrence that, at any dose:

a. Results in death

b. Is life-threatening

The term 'life-threatening' in the definition of 'serious' refers to an event in which the participant was at risk of death at the time of the event. It does not refer to an event, which hypothetically might have caused death, if it were more severe.

c. Requires inpatient hospitalization or prolongation of existing hospitalization (Applies only during the safety follow up period for participants who may have been discharged during the treatment period, ie, between Day 1 and Day 10)

- In general, hospitalization signifies that the participant has been detained (usually involving at least an overnight stay) at the hospital or emergency ward for observation and/or intervention that would not have been appropriate in the physician's office or outpatient setting. Complications that occur during hospitalization are considered AEs. If a complication prolongs hospitalization or fulfills any other serious criteria, the event is serious. When in doubt as to whether "hospitalization" occurred or was necessary, the AE should be considered serious.
- Hospitalization for elective intervention of a pre-existing condition that did not worsen from baseline is not considered an AE.

d. Results in persistent disability/incapacity

- The term disability means a substantial disruption of a person's ability to conduct normal life functions.
- This definition is not intended to include experiences of relatively minor medical significance such as uncomplicated headache, nausea, vomiting, diarrhea, influenza, and accidental trauma (e.g., sprained ankle) which may interfere with or prevent everyday life functions but do not constitute a substantial disruption.

e. Is a congenital anomaly/birth defect

f. Other situations

- Medical or scientific judgment should be exercised in deciding whether SAE reporting is appropriate in other situations such as important medical events that may not be immediately life-threatening or result in death or hospitalization but may jeopardize the participant or may require medical or surgical intervention to prevent one of the other outcomes listed in the above definition. These events should usually be considered serious.
- Examples of such events include invasive or malignant cancers, intensive intervention in an emergency room or at home for allergic bronchospasm, blood dyscrasias or convulsions that do not result in hospitalization, or development of drug dependency or drug abuse.

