4.1 Overall Design

This is an open-label, randomized, multicenter, parallel group, concurrent, controlled study in hospitalized participants with COVID-19 requiring supplemental oxygen (WHO ordinary scale level 4) using a sequential adaptive design to evaluate the efficacy and safety of RESP301 added to standard of care (SOC). Approximately 300 adult (male and female) participants will be consented and randomized 2:1 to the Investigational arm or the Control arm. Participants randomized to the Investigational arm will receive inhaled RESP301 (6 mL) administered using a vibrating mesh nebulizer TID for up to 10 days in addition to the standard of care (SOC) while participants in the Control arm will receive SOC alone.

The study will be divided into the following periods:

- Screening period: starts up to 2 days (48 hours) prior to and extends up to the day of treatment initiation (Day 1); Days -2, -1 and 1
- Intervention period: up to 10 days; Day 1 to Day 10
- Efficacy follow-up: Day 14 and Day 28 (± 2 days)
- Safety follow-up: 28 days after treatment initiation; with the participant being contacted by phone call, if not still hospitalized, on Day 28 (± 2 days)

After screening, eligible participants will be randomized to either RESP301+SOC or SOC alone on Day 1, and the study treatment will be initiated as applicable (Table 1-1). Screening and randomization may happen on the same day (Day 1).

An individual administration of study intervention will be stopped, and supplemental oxygen resumed, if threshold limits of SpO₂ 89% or heart rate 120 beats/min (or as indicated by the Investigator) are exceeded (see Section 4.2 and Section 8.1.2). However, the participant may continue with subsequent doses if the Investigator judges that the benefit / risk ratio remains positive. In this case, the instruction to continue should be duly recorded in the participant's hospital file and the subsequent nebulization should be closely monitored. Inhalation of study intervention should be completed within 20 minutes. A staggered dosing approach will be used for the first 10 participants (up to the first Independent Data Monitoring Committee [IDMC] safety review) to monitor tolerability and response to RESP301 (see Sections 6.1 and 9.6).

The study treatment will be permanently discontinued prior to 10 days if the participant:

- Improves to level 1 or 2 of the modified WHO ordinal scale;
- Progresses to a level > 4 of the modified WHO ordinal scale;

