9.4.5.1 Adverse Events

Adverse Events will be coded using the MedDRA coding dictionary.

The number and percentage of participants with any AE, any related AE, any SAE, any related SAE, any severe AE, and related severe AE as well as the total number of events for each category will be summarized. The number of deaths due to an AE, hospitalization due to an AE, and study discontinuation due to an AE will be summarized.

The number and percentage of participants with an AE, as well as the total number of AEs, will be summarized by SOC and preferred term. This tabulation will be repeated for related AEs, SAEs, related SAEs, severe AEs, and related severe AEs.

All AEs will be provided in patient listings. Patient listings of AEs causing discontinuation of study medication, AEs leading to death, SAEs, related AEs, and severe AEs will be produced.

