- If the SUSAR is fatal or life-threatening, associated with study intervention, and unexpected, regulatory authorities and IECs will be notified within seven calendar days after the Sponsor learns of the event. Additional follow-up (cause of death, autopsy report, and hospital report) information should be reported within an additional 8 days (15 days total).
- If the SUSAR is not fatal or life-threatening but is otherwise serious, associated with study intervention, and unexpected, regulatory authorities and IECs will be notified within 15 calendar days after the Sponsor learns of the event.

The Sponsor will notify the Investigators in a timely fashion of relevant information about SUSARs that could adversely affect the safety of participants. Follow-up information may be submitted if necessary.

The Sponsor will also provide annual safety updates to the regulatory authorities and IECs responsible for the study. These updates will include information on SUSARs and other relevant safety findings.

All SAEs that occur during the study, and all SAEs occurring up to 18 days after receiving the last dose of study intervention, whether considered to be associated with the study intervention or not, must be reported within 24 hours via electronic data collection tool and paper data collection tool to Parexel Safety Services.

The minimum information required for an initial report is:

Name of person sending the report (e.g., name, address of Investigator);

- Participant identification (screening/randomization number, initials, NOT participant name);
- Protocol number;
- Description of SAE;
- Causality assessment, if possible.

However, as far as possible all points on the SAE form should be covered in the initial report, or the completed SAE form itself must be emailed or faxed to the Parexel Safety Services. In addition, the event must be documented in the electronic CRF/EDC system.

After receipt of the initial report, Parexel Safety Services will review the information and, if necessary, contact the Investigator, to obtain further information for assessment of the event. Parexel will be responsible for all information processing and reporting according to local legal requirements. Where necessary, Investigators will inform regulatory authorities in their own countries.

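### The parenthetical in SAE criterion c conflicts with the bullet below it on prolonged stays, and it leaves readmission after a discharge later than Day 10 outside the criterion

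*Protocol*

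**What the plan says.** The text reviewed is Protocol Amendment 1 (Version 2.0). The original protocol carries the same restriction.

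- **Section 10.4.2, criterion c.** The base wording is "Requires inpatient hospitalization or prolongation of existing hospitalization". The parenthetical that follows says "Applies only during the safety follow up period for participants who may have been discharged during the treatment period" and fixes the discharge window: "discharged during the treatment period, ie, between Day 1 and Day 10".
- **Section 10.4.2, first bullet under c.** "If a complication prolongs hospitalization or fulfills any other serious criteria, the event is serious". No period or group is named. The bullet adds that doubt about whether hospitalization occurred or was needed is to be resolved towards serious.
- **Section 10.4.2, lead-in.** An event that is not an AE cannot be an SAE. Admission for signs or symptoms of the disease under study is given as an example.
- **Section 4.1.** Dosing: "Intervention period: up to 10 days; Day 1 to Day 10". Follow-up runs to Day 28 (± 2 days), "with the participant being contacted by phone call, if not still hospitalized, on Day 28", so some participants are expected to be in hospital well after Day 10.
- **Section 10.4.4.** The 24-hour reporting duty covers "All SAEs that occur during the study, and all SAEs occurring up to 18 days after receiving the last dose of study intervention", with no link to discharge date.
- **Section 9.4.5.1.** Any SAE and any related SAE are tabulated, and "The number of deaths due to an AE, hospitalization due to an AE, and study discontinuation due to an AE will be summarized".

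**The concern.** Inclusion criterion 3 (section 5.2) makes every participant an inpatient at entry. A seriousness criterion about hospital stay that works only after discharge is therefore inactive for the whole time RESP301 is being given. Section 7.1 and Table 2-1 name bronchospasm as a risk of inhalation, and section 7.1 lists a methemoglobin level above 3% among discontinuation events. An investigator who finds that such an event has lengthened the stay gets one answer from the parenthetical and the other from the bullet.

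SAE status matters in three ways. It is a safety endpoint (section 3) and a planned table (section 9.4.5.1). It triggers the 24-hour report and feeds SUSAR assessment (section 10.4.4). It also forms part of the safety data from which the IDMC decides, after the first 10 participants, whether intermittent inhalation may be replaced by continuous inhalation (section 6.1). Section 2.2.3 calls the study first-in-man, so a seriousness definition that depends on which line a site reads is an avoidable weakness.

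**Working it through.** No sample size, power or event figure is involved. The check applies the parenthetical to each state a participant can be in and compares the result with the bullet.

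**Step 1: is criterion c ever active on a dosing day?** Participants enter as inpatients (section 5.2). Study treatment stops permanently at level 1 or 2 (section 7.1), and levels 1 and 2 are the non-hospitalized levels (section 8.1.1). A discharged participant is therefore no longer dosed. Since c requires a participant already discharged and in follow-up, it is never active on a dosing day.

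**Step 2: the four states.**

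| Participant state | Criterion c with the parenthetical | Bullet under c |
|---|---|---|
| Inpatient, Day 1 to 10, stay prolonged by an AE | Not active | Serious |
| Discharged Day 1 to 10, readmitted in follow-up | Active | No conflict |
| Still inpatient after Day 10, stay prolonged by an AE | Not active | Serious |
| Discharged after Day 10, readmitted before last follow-up | Not active | Does not address this case |

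Criterion c is active in 1 of 4 states. The prolongation limb survives only if the readmission of someone discharged by Day 10 is itself prolonged.

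**Step 3: which rows are contradictions?** Rows 1 and 3 are: the same event is outside c by the parenthetical and serious by the bullet. Row 4 is a gap. The part of the bullet at issue concerns a complication that prolongs a stay, so it does not conflict with the parenthetical on readmission.

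**Step 4: does the reporting window close the gap?** For a participant dosed through Day 10, 18 days after the last dose is Day 10 + 18 = Day 28, so the window in section 10.4.4 reaches planned last follow-up whatever the discharge date. But it says when an SAE is to be reported, not what counts as one. It neither fills the row 4 gap nor contradicts the parenthetical.

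**Step 5: is the restriction needed to keep the COVID-19 admission out?** No. The lead-in to section 10.4.2 already excludes hospitalization for the disease under study, and section 10.4.1 excludes expected progression unless it is more severe than expected. What the parenthetical additionally removes is events that are AEs.

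**The case against.** The strongest reply is that little is lost in practice. The parenthetical limits only c. Criteria a, b, d, e and f remain in force throughout. Criterion f covers events that jeopardize the participant or need intervention, says these should usually be considered serious, and gives bronchospasm needing intensive treatment and blood dyscrasias among its examples. Section 8.3.6 separately requires SAE reporting of listed disease-related events, such as cough or dyspnea, when they are judged related to treatment or worse than expected. All AEs are collected from consent to last follow-up (section 8.3.1). Related AEs, severe AEs and hospitalization due to an AE are summarized whatever their SAE status (section 9.4.5.1). Intolerance of nebulization and bronchial hyper-responsiveness are separate safety endpoints.

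Most of this stands, and it rules out some stronger readings:

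- A reader might infer that these events cannot be SAEs at all. The text supports only that they are not serious under criterion c.
- A reader might infer that the safety signal disappears. It does not; the events remain in the AE data.
- A reader might infer that the SAE comparison between arms is distorted, because discharge by Day 10 is a post-randomization outcome. That would need the arms to differ in discharge by Day 10, and the documents give no discharge or readmission rates from which to show it.

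The reply does not dispose of the conflict itself. Criterion f relies on investigator judgement, in an open-label study, and section 8.3.6 covers only its listed events. Neither reliably captures an event whose one serious feature is a longer stay or a late readmission.

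**Conclusion.** The point holds as a wording conflict plus a coverage gap in one criterion. On prolongation of an existing stay, the parenthetical and the bullet give opposite answers for anyone still in hospital, both during dosing and after Day 10. On readmission after a discharge later than Day 10, criterion c is silent.

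The consequence is confined to SAE and related-SAE counts, and to 24-hour and SUSAR handling, for events that no other seriousness criterion captures. The documents do not allow that number to be estimated. The primary endpoint, alpha, power and sample size are untouched. It should be fixed, but it does not threaten the trial's main conclusion.

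One assumption concerns the version. Amendment 2 (Version 3.0) supersedes the text quoted here, and the copy available stops before its Appendix 4. Its table of changes lists none to section 10.4.2, only minor language and format changes throughout, so the wording probably persists; this should be confirmed against the full Version 3.0.

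**What to change.** Reconcile the parenthetical with the bullet in section 10.4.2, criterion c, in one of two ways:

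1. Delete the parenthetical. The lead-in already keeps admission for COVID-19 itself from counting.
2. Replace it with a sentence of this kind: *The admission ongoing at enrolment is not itself an SAE; its prolongation by an AE, or any readmission for an AE up to the last follow-up, meets criterion c.*

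The bullet can stay as it is and then agrees with the criterion. The second option is clearer for sites, because it states the likely purpose of the restriction and closes the readmission gap explicitly.

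The cost is one sentence in Appendix 4 and a memo to sites, preferably before the first IDMC review. The downside is somewhat more SAE reports, and investigators will have to judge whether an AE, as opposed to expected COVID-19, lengthened the stay.
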